#### Notes:

- Two AEs with the same PT will be considered as two different events when calculating the “number of events” in the tables.
- Where a subject has the same AE, based on preferred terminology, reported multiple times in the same category the subject will only be counted once at the preferred terminology level in AE frequency tables.
- Where a subject has multiple AEs within the same SOC in the same category, the subject will only be counted once at the SOC level in AE frequency tables.
- AEs where the intensity is missing will be assumed to be “Severe”
- AEs where the causality is missing will be assumed to have “Reasonable possibility of relatedness”

An overall summary of AEs will be provided. The total number of events and number and proportion of subjects experiencing any AEs, TEAEs, TEAEs of special interest, AEs related to study medication (i.e where the investigator has recorded “Reasonable possibility of relatedness”), SAEs, SAEs related to study medication, severe AEs, AEs leading to permanent discontinuation of study treatment and AEs leading to death will be tabulated for each treatment regimen and overall.

Additionally, TEAEs, TEAEs of special interest, related TEAEs, serious TEAEs, related SAEs, AEs leading to permanent discontinuation of study treatment and AEs leading to death will be summarised by SOC and PT for each treatment regimen and overall (number and percentage of subjects experiencing at least one AE per PT as well as the number of observed events per PT). All TEAEs will also be summarised separately by maximum intensity for each SOC and PT and by causality for each SOC and PT.

A table presenting the number and percentage of subjects with at least one AE and the number of AEs for the most common treatment-emergent AEs (reported in  $\geq 1\%$  of patients in any treatment regimen) will be provided. PTs will be used for tabulation, sorted by decreasing overall frequency.

All AEs will be presented in full in a comprehensive listing including subject number, treatment regimen, intensity, seriousness, actions taken, outcome, causality, onset/stop and duration. Details of all TEAEs of special interest, SAEs, AEs leading to permanent discontinuation of study treatment and AEs leading to death will be listed separately.

### 8.7.5 Laboratory evaluations

#### 8.7.5.1 Clinical laboratory

Haematology, blood chemistry, and urinalysis assessments will be conducted at each visit during the treatment phase and Week 60.

The following laboratory parameters will be assessed:

- Blood chemistry
  - Sodium
  - Potassium
  - Chloride
  - Bicarbonate/ $\text{CO}_2$
  - Blood urea nitrogen
  - Creatinine
  - Fasting Glucose
  - Albumin
  - Alkaline phosphatase
  - AST
  - ALT
  - GGT
  - PT/INR
  - Total bilirubin
  - Total protein
  - Calcium
  - Lipid panel (total cholesterol, LDL, HDL, triglycerides)
  - PSA
  - eGFR (calculated based on Cockcroft-Gault formula)
  - eGFR (derived from 4-v MDRD)
- Haematology
  - Red Blood Cell Count [RBC]
  - White Blood Cell Count [WBC]
  - Neutrophils
  - Lymphocytes

- Monocytes
- Eosinophils
- Basophils
- Haemoglobin
- Haematocrit
- Platelets
- Urinalysis
  - Specific gravity
  - pH
  - Protein
  - Bilirubin
  - Glucose
  - Blood
  - Ketones
  - Leukocytes

For the purposes of summarisation in both the tables and listings, all clinical laboratory data will be reported in Standard International (SI) units.

If a lab value is reported using a nonnumeric qualifier e.g., less than (<) a certain value, or greater than (>) a certain value, the given numeric value will be used in the summary statistics, ignoring the nonnumeric qualifier.

Descriptive statistics will be presented for quantitative clinical laboratory parameters for each treatment regimen and time-point. Similarly, changes from baseline (and changes from screening for selected renal parameters; creatinine, urea, and glomerular filtration rate) will be summarised.

The change from baseline in each renal parameter to Week 48 will also be analysed via MMRM in the same manner as the change from baseline in total testosterone (see Section 8.6.3.3).

Values outside the normal range will be categorised as H (above the normal range) or L (below the normal range) based on the laboratory's reference range and these will be flagged in the individual data listings along with the Investigator's assessment.

Qualitative urinalysis parameters (e.g protein, glucose and blood) will only be listed.

### **8.7.5.2 Liver Function**

The number and proportion of subjects with laboratory values for liver function and enzymes of clinical concern as follows will be presented descriptively by treatment regimen:

Parameter	Level for clinical concern
ALT	> 1.5 times the upper limit of the normal range (ULN) > 2xULN > 3xULN > 5xULN > 10xULN
AST	> 1.5xULN > 2xULN > 3xULN > 5xULN > 10xULN
Bilirubin Total	> 2xULN > 3xULN
ALT/AST and Bilirubin Total	ALT/AST > 3xULN and Bilirubin Total > 2xULN (assessments to occur at the same visit)

### 8.7.6 Vital signs

Vital sign assessments will be performed at each visit.

Descriptive statistics (observed values and changes from baseline) will be presented for each treatment regimen and time-point for vital sign measurements (body temperature, pulse rate, systolic blood pressure, diastolic blood pressure, weight and BMI).

The change from baseline in systolic and diastolic blood pressure to Week 48 will also be analysed via MMRM in the same manner as the change from baseline in total testosterone (see Section 8.6.3.3).

Boxplots of observed and change from baseline values by treatment and visit will also be generated for both systolic and diastolic blood pressure.

In addition the number and percentage of subjects meeting each of the criteria below will be presented:

- Normal: SBP < 120 mm Hg and DBP < 80 mm Hg
- Elevated BP:  $120 \leq \text{SBP} \leq 129$  mm Hg and DBP < 80 mmHg
- Hypertension Stage 1:  $130 \leq \text{SBP} \leq 139$  mmHg or  $80 \leq \text{DBP} \leq 89$  mmHg
- Hypertension Stage 2: SBP  $\geq 140$  mm Hg or DBP  $\geq 90$  mmHg
- SBP Change from baseline  $\geq 20$  mmHg
- DBP Change from baseline  $\geq 10$  mmHg

### 8.7.7 Physical examinations

A full physical examination will be performed at Week 36 and Week 48 whereas a limited physical examination (cardiovascular system and lower extremities oedema only) will be performed at all other.

The number and percentage of patients reporting an abnormal physical examination finding (Abnormal CS and Abnormal NCS) will be presented per body system for each treatment regimen and time-point.

In addition the grade of pitting oedema will be summarised descriptively for each treatment regimen and time-point.

### 8.7.8 Electrocardiograms

12-Lead ECG assessments will be performed at Week 36 and Week 48.

Descriptive statistics (observed values and changes from baseline) will be presented for the 12-lead ECG measurements for each treatment regimen and time-point for all ECG parameters (Heart Rate, PR interval, QT interval, RR interval, QRS duration and QTcF interval). In addition, the overall ECG interpretation will be summarised by presenting the number and percentage of subjects with “Normal”, “Abnormal, NCS” and “Abnormal, CS” for each treatment regimen and time-point.

## 8.8 Other analysis

### 8.8.1 DMC

An independent, unblinded external DMC will periodically review accumulating safety data. This will include data evaluation of accumulating unblinded safety data

of BGS649, testosterone monitoring assessment and performing the interim analysis. Full details of composition, operational aspects, and data to be reviewed and recommendation of the DMC is provided in a separate DMC charter and DMC SAP.

#### 8.8.1.1 Testosterone Monitoring

To ensure adequate safety monitoring, serum total testosterone levels will be evaluated at each visit by an independent unblinded physician and if subject meets discontinuation criteria (total testosterone is  $\geq 1500$  ng/dL (52 nmol/L) at any 2 consecutive time points during the study), the subject will be discontinued from treatment. This would also include situation when first testosterone value that meets this threshold of  $\geq 1500$  ng/dL [52 nmol/L] was measured during MBGS205 and consecutive testosterone during study MBGS206.

#### 8.8.1.2 Interim Analysis

No interim analysis is planned for this study.

### 8.8.2 PK analyses

Plasma and Semen PK will be collected at Week 48/EOT only.

BGS649 PK plasma and semen concentrations will be summarised for the PK population by descriptive statistics by treatment regimen and time-point, including the geometric mean and coefficient of variation.

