PK of BGS649 in seminal fluid will also be evaluated after 12 months of study drug exposure. Seminal fluid PK will be assessed (excluding subjects that are vasectomised or have vasectomy planned during the study period) at the Baseline visit (Week 24 of Study MBGS205) and End of Treatment (Visit 7). Subjects that are discontinued early from the study drug will provide samples for seminal fluid PK at the time of the End of Treatment visit, unless they are not able to provide this sample. Simultaneously with semen PK, plasma PK will be assessed to estimate plasma to semen BGS649 transference.

Figure 9–1 Study Design

DMC=data monitoring committee; W=week

During the 24 week treatment period, [redacted] to total of up to 24 doses. The capsule will be taken orally by the subject with water. Subjects receiving active doses of BGS649 in Study MBGS205 will continue with the same dose in Study MBGS206 and the blind will be maintained at randomisation. Subjects receiving placebo in Study MBGS205 will be randomised on a 1:1:1 basis to each of the active treatment arms. If one or more dosing arms are dropped during the conduct of Study MBGS205 these will not be progressed in Study MBGS206 and subjects switching from placebo will be randomly allocated to available dose arms. The safety of the study will be monitored through a DMC and will include relevant subject data from Study MBGS205 and Study MBGS206.

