4. Total testosterone \geq 1500 ng/dL (52 nmol/L) at any 2 consecutive scheduled visits during and in between the both studies MBGS205 and MBGS206. This would also include situation when first testosterone value that meets this threshold of \geq 1500 ng/dL

[52 nmol/L] was measured during MBGS205 and consecutive testosterone during Study MBGS206.

5. Liver laboratory values of:

- ALT or AST > 5 times the ULN

If the increase in ALT or AST is associated with normal bilirubin and ALP, the medical evaluation of withdrawing a subject can be made on a repeat AST/ALT test taken within 48 hours. (Repeated parameters should include: ALT, AST, alkaline phosphatase and total bilirubin). The subject should interrupt study drug until the repeat liver enzymes are available. If repeat liver parameters are all within the normal range, dosing may be continued. If not normalised the subject should be permanently discontinued.

or

- ALT or AST > 3 times the ULN and bilirubin total > 2 times ULN or International Normalised Ratio (INR) > 1.5 or the appearance of worsening fatigue, nausea, vomiting, right upper quadrant pain/tenderness, fever, rash, or eosinophilia
- A hepatic event leading to subject discontinuation should be followed up until event resolution, or becomes not clinically significant

6. Any of the following laboratory abnormalities:

- Renal function values that require discontinuation:
 - Discontinue investigational treatment for a subject if individual serum creatinine increases $\geq 50\%$ compared to Baseline (and is considered clinically significant), or in the event of treatment emergent proteinuria (albumin: creatinine ratio > 300 mg/g or > 30 mg/mmol; protein: creatinine ratio ≥ 500 mg/g or > 50 mg/mmol) (Creatinine can be repeated once within 7 days of initial alert. Study drug administration should be suspended during this time and resumed only if repeat creatinine is back to pre-alert level)
 - A renal event leading to subject discontinuation should be followed up until event resolution (serum creatinine within 10% of Baseline, protein-creatinine ratio within 50% of Baseline), stabilises or becomes not clinically significant, or is assessed as being chronic

7. Subject missed 4 or more consecutive study drug dosing

8. Development of prostate cancer or PSA increase more than 1.4 ng/mL above Baseline level in study MBGS205. It is recommended that in these cases subjects undergo urologic consultation

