11.3 Pharmacokinetic Assessments

Semen Pharmacokinetic sampling

Semen PK sampling for BGS649 will be performed at the following time points (excluding subjects that are vasectomised or have vasectomy planned during the study period), as defined in the schedule of assessments (Table 9-1): Baseline visit (Week 24 of Study MBGS205) and EOT (Visit 7).

Subjects that are discontinued early from the study drug will provide samples for seminal fluid PK at EOT (Visit 7) unless they are not able to provide this sample.

Semen samples for PK analysis will be centrifuged (1000 g × 10 minutes) and the separated seminal plasma will be stored at -20°C until samples are used.

Plasma Pharmacokinetic Sampling

Plasma PK sampling for BGS649 will be performed at the Baseline visit (Week 24 of Study MBGS205) and EOT (Visit 7) to estimate plasma to semen BGS649 transference.

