13.4.2.3 Secondary Pharmacokinetic Endpoint

1. EOT plasma and semen concentration of BGS649 by dose group.

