13.5.3.3 Pharmacokinetics

EOT and FU semen concentration of BGS649 will be summarised by dose group.

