### 6.4 PK population

For the summary of semen concentration of BGS649, all subjects who received at least 1 administration of MBGS206 study medication and have at least 1 quantifiable concentration will be included in the PK population.

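### SAP 8.8.2 leaves out the scheduled Week 24 semen and plasma samples, sets no time-since-dose rule for EOT samples, and excludes men with no quantifiable value, so the by-dose PK summary is incomplete and can be distorted

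*SAP*

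**What the plan says.** **Sampling times.** SAP 8.8.2 says "Plasma and Semen PK will be collected at Week 48/EOT only", and then that concentrations are "summarised for the PK population by descriptive statistics by treatment regimen and time-point". Protocol 11.3 says "Plasma PK sampling for BGS649 will be performed at the Baseline visit (Week 24 of Study MBGS205) and EOT (Visit 7"), and protocol 9.1.1 places semen sampling "at the Baseline visit (Week 24 of Study MBGS205) and End of Treatment (Visit 7"). Protocol Table 9-1 and SAP Table 1 both mark semen and plasma PK in the column of assessments carried over from MBGS205 and again at EOT. SAP section 9, which lists departures from the protocol, is silent on this.

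**Planned summary.** The secondary PK endpoint is "EOT plasma and semen concentration of BGS649 by dose group" (protocol 13.4.2.3). Protocol 13.5.3.3 says "EOT and FU semen concentration of BGS649 will be summarised by dose group". Neither schedule, nor protocol 11.3, has a PK sample at follow-up.

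**Who gives an EOT sample.** Men who stop early give EOT PK samples if they can (protocol 9.1.1, 9.3.4, 11.3), at a visit due within 7 days of discontinuation (9.3.4). One mandatory reason for stopping is "Subject missed 4 or more consecutive study drug dosing" (9.3.4, item 7).

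**Who is summarised.** Under SAP 6.4, men with at least one dose of MBGS206 medication who "have at least 1 quantifiable concentration will be included in the PK population". Protocol 13.3.3 has the same quantifiability condition. Neither document gives a rule for PK values below the limit. The convention in SAP 8.7.5.1 of using the number and ignoring the qualifier is stated for clinical laboratory data.

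**The concern.** The semen and plasma samples are there to describe concentration by dose, and the semen-plasma relationship, so that transfer to sexual partners can be modelled (protocol 7.2.1 and 8.2.2). Three features of the descriptive summary work against that.

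1. For men on active drug since MBGS205, Week 24 is an on-treatment pair at the same dose they continue to take. The SAP sentence writes it out of the report. A man who cannot give semen at EOT may have given it at Week 24.
2. EOT covers both completers and early stoppers. Without a time-since-dose rule, values from men who have been off drug for weeks enter the same dose-group mean as on-treatment values.
3. Requiring a quantifiable value selects the analysis set on the outcome. Removing men with none can only raise the summary, and would bear most on any dose with many low values.

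The second and third features need not act equally across doses, and a by-dose table is read for exactly that comparison.

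**Working it through.** **Sampling times side by side.**

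| Source | Week 24 | EOT | Follow-up |
|---|---|---|---|
| Protocol 9.1.1, 11.3, Table 9-1 | yes | yes | no |
| SAP Table 1 | yes | yes | no |
| SAP 8.8.2 | no | yes | no |
| Protocol 13.4.2.3 (endpoint) | no | yes | no |
| Protocol 13.5.3.3 (analysis) | no | yes | yes |

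SAP 8.8.2 disagrees with SAP Table 1 on collection, and protocol 13.5.3.3 asks for a summary that has no data. For men who were on placebo in MBGS205, Week 24 is a pre-dose sample.

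**Time since last dose (nominal).** Up to 24 weekly doses start at Week 24 (protocol 9.1.1), so the last is at Week 24 + 23 = 47. A completer is sampled 7 days later. After four missed weekly doses the gap is at least 4 × 7 = 28 days, and up to about 28 + 7 = 35 with the 7-day visit rule. Other early stoppers are normally within about 7 + 7 = 14 days.

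**Number of early stoppers.** The synopsis plans 30 entrants per previous active arm, about 25 completers and about 17% dropout. This reproduces: 25/0.83 = 30.1 and 30 × 0.83 = 24.9. About 5 of 30 per arm could therefore give an early EOT sample, for all reasons combined. Only some of them would be 28 or more days from dosing.

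**Illustration, late samples.** The half-life is described only as long (protocol 7.1), so 7 to 42 days is assumed. If a share s of men is sampled 28 − 7 = 21 days later than scheduled, the arm's geometric mean is multiplied by 2^(−s × 21/half-life).

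| Late men | 7 days | 14 days | 42 days |
|---|---|---|---|
| 1 of 30 | 0.93 | 0.97 | 0.99 |
| 5 of 30 (upper bound) | 0.71 | 0.84 | 0.94 |

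**Illustration, men dropped.** Assume log-normal concentrations with σ = √ln(1 + CV²), and a fraction q with no quantifiable value. Dropping the lowest q multiplies the geometric mean by exp(σ φ(z_q)/(1 − q)), where φ is the normal density and z_q the q-quantile. The CV and q are assumptions.

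| CV | q = 1% | q = 10% | q = 30% |
|---|---|---|---|
| 30% | 1.01 | 1.06 | 1.16 |
| 50% | 1.01 | 1.10 | 1.26 |
| 100% | 1.02 | 1.18 | 1.51 |

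**Net direction.** Treat the two effects as multiplicative, at a 14-day half-life and CV of 50%. Five late men with 10% dropped give 0.84 × 1.10 = 0.92. One late man with 30% dropped gives 0.97 × 1.26 = 1.22. The sign depends on quantities the documents do not give.

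**Longest compliant gap.** A 7-day interval, plus 1 day of dosing tolerance, 2 days of visit window and 2 days for semen collection (±48 hours), gives 7 + 1 + 2 + 2 = 12 days.

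**The case against.** The objective and endpoint are both set at end of treatment, so leaving Week 24 out of the table changes no EOT value. A reader might infer that the omission misstates EOT concentration by dose. The documents do not support that, and only information is lost. Nor would tabulating Week 24 as its own time point make the EOT estimates more precise, since nothing is averaged.

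The SAP sentence may mean only that MBGS206 itself collects PK at EOT, the Week 24 sample being carried over from MBGS205. The SAP's introductory notes also send the PK analyses to a separate plan, which may use the Week 24 pairs and time since dose. Both points are fair. Even so, SAP 8.8.2 does specify a descriptive summary with geometric means, and its sentence conflicts with SAP Table 1 for anyone programming from it.

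On late samples, the EOT visit is due within 7 days of stopping, so only the missed-dose rule forces a gap of 28 days; long interruptions or late visits could also produce one. This is a subset. Plasma and semen are taken close together, so a late pair need not distort their ratio.

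On quantifiability, the rule names no matrix in that clause. If plasma can satisfy it, a man with measurable plasma and unmeasurable semen stays in. The gap then is that nothing says how his semen value enters a geometric mean. Nothing in the documents shows that many men will fall below the limit.

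Finally, the summary is descriptive and the protocol calls all analyses exploratory. That limits the consequences but does not remove the contradiction.

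**Conclusion.** The point holds in limited form. It is established from the text that SAP 8.8.2 contradicts protocol 9.1.1 and 11.3 and SAP Table 1 without being listed as a change. It is equally clear that protocol 13.5.3.3 promises a follow-up summary with no scheduled sample, that no rule separates late EOT samples, and that the PK population is selected on having a quantifiable value. The Week 24 omission loses on-treatment pairs for continuing men and does not bias the EOT endpoint.

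Late sampling and the exclusion of unquantifiable men can distort the by-dose pattern. It would be tempting to conclude that the summary does misstate concentration by dose, but that is not shown. The two effects oppose each other, the first touches only a subset, and every percentage above rests on an assumed half-life, CV, below-limit share or number of late men. The correction is still worth making, because the objective is secondary and stated, and the data needed are already planned.

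**What to change.** In SAP 8.8.2:

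- Replace the sampling sentence. Summarise Week 24 (men active in MBGS205 only) and Week 48/EOT by dose and time point, with the within-man semen:plasma ratio.
- Report time since last dose. Show EOT samples within an on-treatment window separately from later ones. The window should be about 12 days. One of a dosing interval plus the visit window, 7 + 2 = 9 days, would exclude semen samples from fully compliant completers.

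In SAP 6.4, define the PK set as dosed men with at least one evaluable sample. Give the number below the limit by dose and matrix, and present the median with those men counted as the lowest values. The median is estimable as long as fewer than half of a group are below the limit.

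In protocol 13.5.3.3, delete the follow-up summary. Record the reconciliation in SAP section 9, and check it against the separate PK plan.

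The cost is SAP wording, one protocol correction and minor programming. The samples are already scheduled, and dose dates and times are recorded under protocol 10.4. The downside is a slightly longer table and a lower N in the on-treatment EOT row.

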### 8.8.3 Association Testing

To determine any correlation between endpoints after 12 months active treatment, various association testing will be conducted using the ITT Population in subjects that were randomised to active treatment in Study MBGS205 at Week 48. For the below sets of endpoints separate linear regression models in which changes in PRO measure total or subscale scores will be taken as the predictor variable, associated PRO baseline score as a covariate and the endpoint to be tested against as the regressor variable. Pearson's Correlation coefficients, coefficients of determination ( $R^2$  statistic) Beta coefficients, standard errors, and 95% CIs will be presented. In addition scatter graphs will be generated annotated with the coefficient of determination ( $R^2$  statistic):

- Change in PRO measures vs Change in Body Composition Parameters
- Change in PRO measures vs Change in Bio Impedance Parameters
- Change in PRO measures vs Change in Physical Activity Parameters
- Change in PRO measures vs Change in Grip Strength
- Change in PRO measures vs Change in Sleep Parameters
- Change in PRO measures vs Change in Oestradiol
- Change in PRO measures vs Change in Testosterone/oestradiol Ratio

Similar association testing will be conducted on the below endpoints using total testosterone as the predictor variable:

- Change in Total Testosterone vs Change in Cardiometabolic parameters
- Change in Total Testosterone vs Change in Body Composition parameters
- Change in Total Testosterone vs Change in Bio Impedance Parameters
- Change in Total Testosterone vs Change in Physical Activity Parameters
- Change in Total Testosterone vs Change in Grip Strength
- Change in Total Testosterone vs Change in Sleep Parameters
- Change in Total Testosterone vs Change in PRO measures

Association testing will also be conducted on the below

- Change in systolic blood pressure vs Total Testosterone, Oestradiol and Testosterone/Oestradiol ratio at Week 48
- Change in diastolic blood pressure vs Total Testosterone, Oestradiol and Testosterone/Oestradiol ratio at Week 48
- Change in Creatinine vs Blood Pressure (Absolute systolic and diastolic blood pressure) at Week 48
- Change in Creatinine vs Change in Blood Pressure (Systolic and Diastolic blood pressure) at Week 48

---

